## 9.4.4.2.1. Reporting of SAEs

All SAEs must be reported to the Safety Contact person(s) within 24 hours of first becoming aware of the SAE. The Investigator must complete an SAE Form, including a detailed description of the SAE and all other information available (e.g., hospital records, autopsy reports and other relevant documents). The Investigator must inform the IRB about such AEs in accord with ICH guidelines and the practices of the governing IRBs (Section 5.1.).

Follow-up information, or new information available after the initial report, should be actively sought and reported to the Sponsor as it becomes available using the SAE Form.

Safety Contact persons and all contact information are listed in the Site Manual and/or Regulatory Binder provided to each investigational site.

## 9.4.4.2.2. Other Events Requiring Immediate Reporting

The Investigator must report a pregnancy that occurs in a subject during a clinical study to the Medical Monitor within 24 hours of first becoming aware of the event. The Investigator should discuss the case with the Medical Monitor; the Investigator must follow any pregnant subject for 3 months after the child is born. Any AEs concerning the pregnancy of the subject during pregnancy or the child after birth must be documented and reported to the Sponsor.

# 9.4.4.2.3. Expedited Reporting

The Sponsor will inform Investigators and regulatory authorities of reportable events, in compliance with applicable regulatory requirements, on an expedited basis (i.e., within specific timeframes). For this reason, it is imperative that investigational sites submit SAE information to the Sponsor (or designee) in the manner described above.

## 9.4.4.3. Laboratory Measurements

Clinical laboratory tests will be performed by a central laboratory. Information regarding collecting, handling, and shipping samples will be detailed in a separate manual. The Schedule of Visits and Procedures (Table 1. Schedule of Visits and Procedures) shows the time points at which blood and urine will be collected for clinical laboratory tests.

For subjects who participate in the optional PK portion of the study, a total of approximately 32mL (8 PK blood draws  $\times$  4mL) of blood/subject will be taken during the course of the study for the purpose of PK samples, in addition to 29mL (2 blood draws for clinical chemistry  $\times$  14.5mL) required for laboratory tests for all subjects. A complete list of all clinical laboratory assessments is presented in Table 2. Clinical Laboratory Assessments.

Laboratory personnel contact information and laboratory sample shipment information and instructions are listed in the Site Manual and/or Regulatory Binder provided to each investigational site.

Hematology	Serum Chemistry	Urinalysis			
Hematocrit Hemoglobin Red blood cell count (RBC) Platelet count White blood cell count (WBC) (with differential)	Albumin Alkaline phosphatase Alanine transaminase (ALT) Aspartate transaminase (AST) Bilirubin- Total and Direct Blood urea nitrogen (BUN) Calcium Chloride Cholesterol- Total, HDL and LDL Creatinine Creatine phosphokinase (CPK) Gamma-glutamyl transpeptidase (GGT)	Ketones Protein Specific gravity Glucose pH			
	Glucose Inorganic phosphorous Potassium Sodium Total protein Triglycerides Uric acid				
Other tests					
	ouse (amphetamines, barbiturates done, opiates, phencyclidine, proj ?)				

### Table 2. Clinical Laboratory Assessments

CYP2D6 enzyme activity (poor, intermediate and ultra rapid metabolizers)

Abnormal lab findings may be confirmed if necessary by one repeated testing at the discretion of the Investigator. Any laboratory abnormality may qualify as an AE in the Investigator's judgment.

## 9.4.4.4. Vital Signs, Height, and Weight Measurements

Vital sign measurements (HR, blood pressure, temperature, and respiratory rate) will be obtained at all visits as designated on the Schedule of Visits and Procedures (Table 1. Schedule of Visits and Procedures). Blood pressure and pulse will be measured after the subject has been sitting for 5 minutes. Height and weight will be obtained at the Screening Visit and weight will be collected at all visits as designated on the Schedule of Visits and Procedures (Table 1. Schedule of Visits and Procedures).

# 9.4.4.5. Medical, Psychiatric History and Physical Examinations

Medical and psychiatric history, including smoking history, will be taken at the screening visit. Physical examinations will be performed at the Screening Visit and Final Visit as designated on the Schedule of Visits and Procedures (Table 1. Schedule of Visits and Procedures).

# 9.4.4.6. Electrocardiograms (ECGs)

ECGs (12-lead) will be obtained at the Screening Visit, Visit 4, and the Final Visit as designated on the Schedule of Visits and Procedures (Table 1. Schedule of Visits and Procedures). Additional ECGs may be performed at other times if deemed necessary.

The ECG will be recorded while the subject is resting in a supine position. The ECG will electronically measure the PR, QRS, QT, and QTc intervals, and heart rate.

All ECG tracings will be reviewed within 24 hours by the Investigator or qualified Sub-Investigator. PR intervals will be determined for each of these ECGs from a single reading. Invalid measurements will be repeated. QTc will be reported as QTcF (QT corrected using Fridericia's method).

## 9.4.5. Completion/Discontinuation of Subjects

Subjects will be permitted to leave the study at any time. Subjects can be withdrawn from the study in any of the following circumstances:

- SAE or an AE
- Administrative reasons (e.g., sponsor decision)
- Withdrawal of consent/assent
- If the subject becomes pregnant
- If it is in the best interest of the subject, in the opinion of the Investigator
- Termination of the study

When an event such as a family emergency, a transient illness (such as a cold) unrelated to SM, or a remediable act of non-compliance prevents a subject from participating in a scheduled visit, but the subject wishes to continue in the study, the Investigator will attempt to reschedule the visit and retain the subject in the study on a case by case basis, rather than discontinue the subject's participation.

If a subject is prematurely discontinued from participation in the study for any reason after SM administration, the Investigator must make every effort to perform the Final Visit assessments.

## 9.5. Treatments

#### 9.5.1. Treatments Administered

SM will be dispensed at each visit during the Randomization and Dose Treatment Periods. Subjects will receive a bottle at each visit containing the correct number of 50mg (or placebo) capsules, which is a sufficient number of capsules for dosing until the next visit. The SM will be taken by the subject orally, three times per day during waking hours, with at least 4 hours between doses (morning, noon, and evening).

At Visit 8, subjects who agree to participate in the optional PK sub study will be given 2 x 50mg SPN-812V capsules on-site in the morning, unless the subject had been down-titrated, in which case, the subject will receive 1 x 50mg SPN-812V capsule on-site in the morning. Note: all subjects who participate in the optional PK sub study will be given active SPN-812V capsule(s) in this portion. For subjects not participating in the optional PK sub study, their last dose will be taken the evening before the End of Study Visit (Visit 8).

#### 9.5.2. Identity of Study Medication

SM are supplied as size 0 white opaque capsules by the Sponsor in labeled bottles. There will be 50 capsules per bottle. Labels will bear the protocol number, product code, and batch number. SM will be repackaged each week into a weekly supply by the unblinded site staff member who will be dispensing the blinded medication. The site number, subject number, subject initials, and the number of capsules to be taken at each dose per day, will be handwritten on the labels by the unblinded staff member who will be dispensing the blinded medication.

### 9.5.3. Handling of Study Medication

All SM will be supplied to the Investigator by the Sponsor. SM supplies must be kept in an appropriate secure area (e.g., locked cabinet) and stored according to the conditions specified on the SM labels. The Investigator must maintain an accurate record of the shipment and dispensing of the SM in an accountability log, a copy of which must be given to the Sponsor at the end of the study. An accurate record of the date and amount of SM dispensed to each subject must be available for inspection at any time. The assigned unblinded CRA will review these documents on one or more visits to the investigational site.

All SM supplies are to be used only for this protocol and not for any other purpose. The Investigator must not destroy any SM labels or any partly used or unused SM supply. At the conclusion of the study and as appropriate during the course of the study, the Investigator will return all used and unused SM containers and a copy of the completed SM accountability log to the Sponsor.

### 9.5.4. Study Medication Accountability

The Investigator, who will be blinded, will delegate responsibility to a qualified unblinded study staff member who will be responsible for the accountability of all clinical supplies (receipt, dispensing, inventory, record keeping, and return) following Sponsor

instructions and must adhere to GCP guidelines as well as municipal, state, and federal regulations.

Under no circumstances will the Investigator or the delegated unblinded staff member allow the SM to be used other than as directed by this protocol. Clinical supplies will not be dispensed to any individual who is not enrolled in the study.

An accurate and timely record of the receipt of all clinical supplies, dispensing of SM to the subject, collection of unused supplies returned by the subject at each visit, and subsequent return of unused SM to the Sponsor must be maintained. This includes, but may not be limited to: (a) documentation of receipt of clinical supplies, (b) SM dispensing/return reconciliation log, (c) SM accountability log, and (d) all shipping service receipts. All forms will be provided by the Sponsor. Any comparable forms that the investigational site wishes to use must be approved by the Sponsor. Discrepancies on SM accountability must be documented and addressed by the delegated unblinded staff member.

The supplies and inventory records must be made available, upon request, for inspection by the designated representative of the Sponsor or a representative of the Food and Drug Administration (FDA). All unused SM, including empty containers, are to be returned to the Investigator by the subject or parent or LAR, and ultimately to the Sponsor at the conclusion of the study, unless provision is made by the Sponsor for destruction of supplies and containers at the investigational site. Upon completion of SM accountability and reconciliation procedures by investigational site personnel and documentation procedures by Sponsor personnel, SM that is to be returned to the Sponsor must be shipped following all local regulatory and shipment laws. Forms and information that could unblind the study must be maintained such that the Investigator and blinded study staff are not unblinded.

### 9.5.5. Method of Assigning Subjects to Treatment Groups

The randomization for this study will be managed centrally; specific instructions to conduct subject randomization will be provided in a separate document to all investigational sites.

A randomization scheme will be generated using a pseudo-random number generator in a computer program. The method avoids bias by use of a chance mechanism. The randomization scheme assigns Treatment 1 or Treatment 2 to each randomization number in a 1:1 ratio.

Upon admission to the study, subjects will be assigned a 4-digit screening number, in the order that they are entered. Subjects who subsequently meet all eligibility criteria will be assigned a 6-digit randomization number. The first 3 digits will refer to the site, and the last 3 will refer to the subject-specific number, which will be assigned according to the randomization scheme.

Once a randomization number has been assigned, no attempt should be made to use that number again, if, for example, a subject is withdrawn. All subjects are randomized only once.

Note: all subjects who participate in the optional PK substudy will be given active SPN-812V capsule(s) in this portion.

#### 9.5.6. Removal of Subjects from Therapy or Assessment

The Investigator or subjects themselves may stop SM treatment at any time for safety or personal reasons. If possible, a subject who discontinues treatment will be followed for end of study protocol-specified visits and procedures. A subject removed from the study for any reason may not be replaced.

### 9.5.7. Dosing Schedule

At the Baseline and Randomization Visit, subjects will be randomized to Treatments 1 or 2 and will initiate dosing. Once the target dose is reached, maintenance treatment will continue for 6 weeks. Down titration to the starting dose is allowed for subjects who cannot tolerate the maintenance dose, at the discretion of the Investigator in consultation with the Medical Monitor. Subjects who cannot tolerate study drug after dose-reduction should be removed from the study.

At Visit 8, subjects who agree to participate in the optional PK sub study will be administered efficacy assessments prior to dosing. Then, subjects will be given 2 x 50mg SPN-812V on-site in the morning, unless the subject had been down-titrated, in which case, the subject will receive 1 x 50mg SPN-812V on-site in the morning.

#### 9.5.8. Method of Administration

Capsules should be swallowed whole and not crushed or chewed. The SM will be administered three times per day, with at least 4 hours between doses (morning, noon, and evening). When possible, doses should be administered at the same times each day. If a dose is missed, it should be taken as soon as possible unless it is within 30 minutes of the next dose; in this case the subject should skip the missed dose and return to the regular schedule thereafter.

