## 7. INTRODUCTION

Viloxazine was previously marketed as an antidepressant in several European countries, since the 1970's, and is currently under development by the Sponsor as SPN-812V, for its potential utility in treating adult attention deficit hyperactivity disorder (ADHD). Viloxazine is a racemate and Supernus plans to develop the compound as such. Supernus intends to carry out this preliminary safety and proof of concept study in adult ADHD patients using an immediate release formulation that will support future development of a modified release formulation to facilitate compliance and possibly improve tolerability.

Similar to tricyclic antidepressants and atomoxetine, viloxazine is an inhibitor of the reuptake of norepinephrine, but may also enhance the release of serotonin from neuronal stores. Clinical efficacy in Major Depressive Disorder has been shown at daily doses of 300 to 600 mg. Thorough published pharmacological and clinical summaries of the product are found in the reviews of Pinder et al., 1977 and Ban et al., 1980.

Supernus development thesis is based on the current unmet medical need for effective longacting non-stimulant treatment for ADHD in adults. Viloxazine can offer a compelling alternative to the use of scheduled substances to control ADHD thus limiting patients' exposure to agents with potential for substance abuse. This Phase I/IIa study seeks to evaluate the safety and tolerability of an immediate release formulation of viloxazine given three times per day (TID) at a dose of 150 or 300mg/day in adults. A randomized, multicenter, parallel group, double-blind, placebo-controlled dose-ranging study design will be used. 50 subjects will be randomized; assuming a 20% dropout rate, it is anticipated that 40 subjects will complete the study. Subjects will be monitored regularly for safety endpoints.

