## 9.4.3. Pharmacokinetic Measurements

On the morning of Visit 8, all subjects who wish to participate in the optional PK day will arrive at the clinic after an overnight fast and will have all efficacy assessments administered first. The subjects then will have a pre-dose PK sample taken, and be administered either 2 x 50mg SPN-812V capsules or will be administered 1 x 50mg SPN-812V capsule for subjects who underwent dose reduction. PK sampling will occur pre-dose and at 0.5, 1, 2, 3, 4, 5, and 6 hours post-dose. Although there is a 30 minute window on draw times, efforts should be made to ensure that the time interval between any two sampling timepoints is not less than 30 minutes. Subjects may eat two hours after dosing.

SPN-812V concentrations in plasma samples will be determined by the Sponsor using a validated chromatographic method. The amount of blood to be drawn at each timepoint to determine the plasma concentrations of SPN-812V is 4mL. Information regarding sample collection, handling, and shipping procedures will be detailed in a separate manual.

Single dose administration of viloxazine hydrochloride (100mg) to ten healthy volunteers resulted in mean  $C_{max}$  near 1800 ng/mL for viloxazine at a mean  $T_{max} \sim 100$  min post-dose and with elimination half-life ~3 hr (Vandel B. et al., "Pharmacokinetics of viloxazine hydrochloride in man," European Journal of Drug Metabolism and Pharmacokinetics, 1982, Vol 7, pp. 65-68). Timepoints were chosen on the basis of these data to inform both absorption and elimination phases of the viloxazine time course while minimizing the sampling burden on patients. The design of the study provides both first-dose (in placebo group) and steady state (in active group) observations, albeit in parallel treatment groups.

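### The missed-dose rule in Protocol 9.5.8 allows two doses about 31 minutes apart, against the protocol's own 4-hour minimum

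*Protocol*

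**What the plan says.** Three instructions bear on the interval between doses.

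- **Minimum interval.** Protocol 9.5.1 has the medication taken "three times per day during waking hours, with at least 4 hours between doses (morning, noon, and evening"). Protocol 9.5.8 repeats the limit: three times daily, "with at least 4 hours between doses (morning, noon, and evening").
- **Clock times.** Protocol 9.5.8 adds: "When possible, doses should be administered at the same times each day".
- **Missed dose.** Protocol 9.5.8 continues that a missed dose is to be taken as soon as possible "unless it is within 30 minutes of the next dose". Only inside those 30 minutes is the missed dose skipped and the usual schedule resumed.

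For a late dose that is taken, neither section says what happens to the next one. The SAP has no missed-dose rule.

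**The concern.** The missed-dose sentence is the specific instruction for a common event, so a subject or site would naturally follow it. It uses 30 minutes as the test of whether a late dose is too close to the next one, while the surrounding text sets 4 hours. Nothing ranks the two rules.

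Safety is the primary objective. Subjects who cannot tolerate the study dose are reduced to the starting dose or leave the study. An avoidable concentration peak could therefore bear on what the trial measures. It would also be hard to recognise afterwards: the only dose-time diary planned for subjects is the one given at Visit 7 to participants in the optional PK sub-study (Protocol 9.1.2 and Table 1). A compliance rate based on capsule counts would not show it either, because the number of capsules taken is the same.

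**Working it through.** **1. The interval, from the text alone**

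- Required minimum: 4 h = 240 min (9.5.1, 9.5.8).
- Cut-off for skipping: 30 min before the next dose (9.5.8). A dose remembered 31 min before the next one is therefore to be taken.
- Shortfall: 240 − 31 = 209 min. The gap is 31/240 = 13% of the minimum.
- Amount at the study dose (2 x 50 mg per intake): 2 x 100 = 200 mg within 31 min.

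**2. How far the conflict reaches**

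The protocol fixes no clock times, so assume scheduled doses are 4, 5 or 6 h apart. The rules diverge when a dose is late by (spacing − 4 h) up to (spacing − 0.5 h):

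| Assumed spacing | Lateness at which the rules conflict | Share of the interval |
|---|---|---|
| 4 h | 0 to 3.5 h | 3.5/4 = 88% |
| 5 h | 1 to 4.5 h | 3.5/5 = 70% |
| 6 h | 2 to 5.5 h | 3.5/6 = 58% |

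These are shares of clock time, not probabilities.

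**3. Illustration of size**

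Inputs from Protocol 9.4.3, for a single 100 mg dose: Cmax about 1800 ng/mL, Tmax about 100 min, half-life about 3 h. Assumed: linear kinetics, and one compartment with first-order absorption.

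- ke = ln 2 / 3 = 0.231 per h.
- ka solves ln(ka/ke)/(ka − ke) = 100/60 h, which gives ka = 1.238 per h.
- Concentration after one dose is proportional to exp(−ke·t) − exp(−ka·t), scaled so that the peak is 1800 ng/mL.

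Two doses on their own peak at about 3566 ng/mL when 31 min apart and 2710 when 4 h apart, a ratio of 1.32.

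For repeated dosing, six days of 100 mg three times daily from 08:00 were superposed. One dose on the last day was then moved to the stated gap before the next. Peaks are in ng/mL, with the change from the scheduled peak:

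| Scenario | 4 h spacing | 5 h spacing | 6 h spacing |
|---|---|---|---|
| As scheduled | 3106 | 2768 | 2526 |
| Noon dose 31 min before evening dose | 3950 (+27%) | 3811 (+38%) | 3724 (+47%) |
| Noon dose 2 h before evening dose | 3624 (+17%) | 3478 (+26%) | 3387 (+34%) |
| Noon dose 3 h before evening dose | 3347 (+8%) | 3202 (+16%) | 3111 (+23%) |
| Morning dose 31 min before noon dose | 3602 (+16%) | 3607 (+30%) | 3614 (+43%) |
| Same late noon dose as in the second row, evening dose delayed to 4 h after it | 3122 (under +1%) | 2822 (+2%) | 2783 (+10%) |

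In the last row the evening dose falls at 19:29, 21:29 or 23:29. At 6 h spacing that may be outside waking hours, so skipping would apply. The figures in that row include the following day.

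**4. Context**

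The protocol's Introduction states: "Clinical efficacy in Major Depressive Disorder has been shown at daily doses of 300 to 600 mg". By linearity, 600 mg/day given three times daily (assumed) peaks at twice the scheduled values: about 6210, 5540 and 5050 ng/mL.

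**The case against.** The best counter-reading rests on the force of the words. The 4-hour minimum is stated as what will happen; fixed clock times apply only where possible, and the missed-dose rule is phrased as what should happen. On that reading the 4-hour minimum governs, the late dose is taken, and the next dose moves. Resuming the usual schedule is mentioned only for the skipped dose, so nothing expressly tells a subject who took a late dose to keep the next clock time. This reading is possible and satisfies every rule. But the protocol does not state it, and on it the 30-minute cut-off has little purpose: if the next dose always moves, closeness to its scheduled time hardly matters.

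Several points about consequence do stand. The largest increases need a dose remembered almost exactly 31 minutes before the next, which is then taken on time. The model's form and the spacings are assumed, and its inputs are single-dose means from ten healthy volunteers. The total daily dose stays at 300 mg, and the worst peak, about 3950 ng/mL, is below the modelled 600 mg/day peaks. The rule is the same in both arms, and no test or analysis population changes. The subject instructions are not among the documents and may already say to delay the next dose. These points limit the importance of the conflict; they do not remove it from the protocol text.

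**Conclusion.** The concern holds. As written, the missed-dose sentence allows a gap of about 31 minutes where the protocol requires 240, and gives no instruction that would prevent it. This follows from the text and depends on no model.

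The worst-case rise in peak of 27% to 47% is an illustration. It rests on linear one-compartment kinetics, the single-dose values in 9.4.3 and assumed spacings of 4 to 6 hours; at less extreme gaps it is smaller. The effect on adverse-event rates cannot be quantified, because the documents give neither how often doses are missed nor a relation between exposure and adverse events. The point concerns a dosing instruction in a trial whose primary objective is safety. It should be corrected, but it does not threaten the efficacy analysis or any statistical figure in the plan.

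**What to change.** Replace the 30-minute cut-off in Protocol 9.5.8 with wording that agrees with the 4-hour minimum, for example:

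> Take a missed dose as soon as you remember it, and delay the following dose if needed so that 4 hours or more separate the two. If this cannot be done within waking hours, omit the missed dose and take the next one at its usual time.

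Use the same text in the subject instructions. The cost is one sentence in each place, and a few more doses may be delayed or skipped.
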